### **5.9.4 Expected drop-out rates**

Factors affecting possible drop-out rates include the option to withdraw participation at any time.

It is anticipated that a subject's inclination to withdraw at procedure-time will be minimal, as prostate biopsy is indicated regardless of the assigned imaging modality.

### **5.9.5 Pass/fail criteria**

The primary outcome of the study will fail if micro-ultrasound targeted biopsy fails to identify cancer in significantly more subjects than mpMRI targeted biopsy. This will be quantified by testing against the lower one-sided 95% confidence interval bound of the ratio of the two sensitivities, which must not be less than 76%.

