### ***5.7.2 Hypothesis***

**Primary Hypothesis:** Micro-ultrasound provides non-inferior (10% margin) sensitivity to detect csPCa using targeted samples compared to mpMRI.

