## 5.9 Statistical considerations

### 5.9.1 Statistical design, method and analytical procedures

Case data will be analyzed by an independent third-party biostatistician using a statistical modeling software tool (PASS or MATLAB).

The primary endpoint is the relative detection rate (sensitivity) between mpMRI and micro-ultrasound for significant prostate cancer at a subject level. Power is based on the sensitivity of the test. Prevalence is assumed to be 60%.

H0: Sensitivity of micro-ultrasound/Sensitivity of mpMRI  $\leq \delta = 0.76$

H1: Sensitivity of micro-ultrasound/Sensitivity of mpMRI  $> \delta = 0.76$

where  $\delta$  was based on results of comparing mpMRI to TRUS as noted below.

Specificity will be similarly tested. That is:

H0: Specificity of micro-ultrasound/ Specificity of mpMRI  $\leq \delta = 0.67$

H1: Specificity of micro-ultrasound/ Specificity of mpMRI  $> \delta = 0.67$

These analyses will be conducted at the subject level.

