#### Non-inferiority Margin, $\delta$

In the PROMIS study, the most recent confirmatory study of mpMRI to TRUS, mpMRI showed improvement in sensitivity of MP-MRI to TRUS from 0.93 to 0.48, respectively, with a test ratio of 0.52 (95% CI: 0.45-0.60) using McNemar's test. In order to preserve the effect of mpMRI versus TRUS as seen in this study, the non-inferiority margin for the test ratio of 0.76 (24%) was chosen as being equal to 50% of the effect from the point estimate of 0.52 to a ratio of unity (equal sensitivity). Then, the lower bound of the test ratio must not exceed 0.76 in order for non-inferiority to be declared in the current trial, thus preserving at least 50% of the effect of mpMRI versus TRUS. McNemar's test will be used to establish the (1- $\alpha$ ) confidence interval for the test ratio.

Specificity from the same study was lower on mpMRI than TRUS with a test ratio of 2.34 (2.08–2.68). In the prostate biopsy procedure, since sampling is required regardless of imaging outcome (systematic sampling), specificity is less important. Still, we would like to preserve a reasonable specificity similar to mpMRI, therefore we select a non-inferiority margin of 0.67, or not more than 50% worse than the existing difference between mpMRI and TRUS (2.34\*1.5 ratio to TRUS, 1/1.5=0.67 ratio to mpMRI).

Details of the design are presented in section 5.8.1.

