### **5.9.3 Level of significance and power of the clinical investigation**

Assuming a micro ultrasound sensitivity of 0.85 and mpMRI performs at an expected 0.90 sensitivity, then 120 subjects would be required to provide 80% power to reject the null hypothesis, assuming 80% agreement between the methods.

PASS and MATLAB software were used for sample size calculations.

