Sensitivity of mpMRI has varied widely in the literature as demonstrated by numerous meta-analyses, showing detection rates ranging from 24%-87%. The PROMIS trial found a sensitivity of 88% for predicting clinically significant prostate cancer, but did not perform targeted biopsy. Therefore, this value could be seen as a maximum possible when perfect targeting and histopathology is assumed. In cases with targeted biopsy, such as the PRECISION trial, mpMRI detected significant cancer in 38% of the arm vs. 26% in the systematic biopsy arm. Assuming a similar 54% incidence this amounts to sensitivities of 70% and 48% respectively which compare well with our own feasibility cohorts demonstrating sensitivities of 56-85% for mpMRI and previously discussed sensitivity data for systematic biopsy.

Sensitivity data on micro-US is available from 2 cohort studies and 1 randomized trial. These three datasets suggest sensitivities of 83% (N=60), 98% (N=79), and 61% (N=286) for a weighted average of 71%. While this average is biased towards the earlier data from the randomized trial, this study was conducted on an early version of the device with little training on the PRI-MUS risk identification protocol, therefore we expect this to underestimate the true sensitivity of the micro-US modality.

Given an incidence of approximately 50% with sensitivities of mpMRI and Micro-US of approximately 66% and 75% respectively, 108 subjects are required to provide 80% confidence of achieving non-inferiority within 20%. This non-inferiority bound was chosen to maintain at least 50% of the benefit of mpMRI over conventional systematic biopsy providing a sensitivity of approximately 48%.

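### The primary success rule contradicts itself: a 10% non-inferiority margin in the primary hypothesis, a sensitivity ratio of 0.76 in the statistical section, and two sentences that mis-state the 0.76 rule

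*Combined protocol and SAP*

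**What the plan says.** - **5.7.2 Hypothesis.** The only statement labelled as the primary hypothesis reads: "Micro-ultrasound provides non-inferior (10% margin) sensitivity to detect csPCa using targeted samples compared to mpMRI". It does not say whether 10% is a difference in percentage points or a relative loss.
- **5.9.1, hypotheses.** The alternative is written on the ratio scale, "H1: Sensitivity of micro-ultrasound/Sensitivity of mpMRI", and set above δ = 0.76.
- **5.9.1, Non-inferiority Margin.** The 0.76 is derived as half the distance from a ratio of 0.52 (TRUS to mpMRI) to 1, and is labelled 24%. The decision sentence then says that "the lower bound of the test ratio must not exceed 0.76 in order for non-inferiority to be declared in the current trial", and continues "thus preserving at least 50% of the effect of mpMRI versus TRUS". McNemar's test is named as the source of the confidence interval.
- **5.9.5 Pass/fail criteria.** The first sentence reads: "The primary outcome of the study will fail if micro-ultrasound targeted biopsy fails to identify cancer in significantly more subjects than mpMRI targeted biopsy". The second reads: "This will be quantified by testing against the lower one-sided 95% confidence interval bound of the ratio of the two sensitivities", and requires that bound to be no lower than 76%.
- **5.9.3 Power.** With sensitivities of 0.85 and 0.90, "120 subjects would be required to provide 80% power to reject the null hypothesis, assuming 80% agreement between the methods".
- **5.20 Critical Literature Review.** A further margin of 20%, also without a scale, is used to size a trial of 108 subjects. It is not offered as a success rule.

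**The concern.** The primary hypothesis and the formal test carry different margins, and no sentence gives one precedence. They are not two expressions of the same quantity, because the plan itself calls the 0.76 ratio a 24% margin. A report could declare success under 5.9.1 and 5.9.5 on data that fail the margin in 5.7.2. A critic could then say that the hypothesis was not met, or that the lenient margin was picked afterwards.

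Two more sentences give a wrong answer if followed literally. The opening of 5.9.5 asks for superiority, although the plan assumes micro-ultrasound to be the less sensitive method. The margin subsection would declare non-inferiority when the lower bound is at or below 0.76, which reverses the alternative hypothesis.

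**Working it through.** **Inputs.** From 5.9.3: 120 subjects, sensitivities 0.85 (micro-ultrasound) and 0.90 (mpMRI), 80% agreement. From 5.9.1: prevalence 60%, so 120 × 0.6 = 72 expected cases. From 5.9.5: one-sided 95% bound. Assumption: the 80% agreement applies among cases, so 20% of case pairs are discordant. The cell probabilities are then both positive 0.775, micro-ultrasound only 0.075, mpMRI only 0.125, neither 0.025.

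**The margin reproduces.** 0.52 + 0.5 × (1 − 0.52) = 0.76.

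**The two margins on one scale.** At mpMRI sensitivity 0.90, a ratio of 0.76 allows 0.76 × 0.90 = 0.684, a loss of 21.6 points. A 10% margin allows 10 points, or 9 points if relative (0.10 × 0.90). A 24% relative loss equals 10 points only if mpMRI sensitivity is 0.10 / 0.24 = 0.417, below the planning value of 0.90 and below the 56–85% that 5.20 quotes from the feasibility cohorts.

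**The stated power does not reproduce.** Paired log-ratio at 72 cases:

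- SE = √[0.20 / (72 × 0.85 × 0.90)] = 0.0603
- Distance to the margin = ln(0.85/0.90) − ln(0.76) = 0.2173
- 0.2173 / 0.0603 − 1.645 ≈ 1.96, or 97.5% power

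Simulation gives 93% to 95%. Either way it is above the plan's 80%.

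**Chance of success under each rule.** 400,000 simulated trials, number of cases drawn as Binomial(120, 0.6), one-sided 5%:

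| Rule | Score | Wald |
|---|---|---|
| Ratio above 0.76 | 93.3% | 95.5% |
| Loss below 10 points | 23.0% | 26.4% |
| Ratio above 0.90 | 18.2% | 22.2% |
| Superiority (ratio above 1) | about 0.5% | about 0.5% |
| Pass 0.76, fail 10 points | 70.3% | 69.1% |
| Pass 0.76, fail ratio 0.90 | 75.1% | 73.3% |

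**One dataset near the expected result.** 72 cases: 56 both, 5 micro-ultrasound only, 9 mpMRI only, 2 neither.

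- Ratio = 61/65 = 0.938. Wald lower bound = exp[ln 0.938 − 1.645 × √(14 / (61 × 65))] = 0.851; score lower bound 0.841.
- Difference = −4/72 = −5.6 points. Wald lower bound = −0.0556 − 1.645 × √[(14/72 − (4/72)²) / 72] = −14.0 points.

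These data pass 0.76 and fail 10% on either scale.

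**Size needed if 10% is meant (80% power, closed form).**

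- 10 points: (1.645 + 0.842)² × (0.20 − 0.05²) / 0.05² = 489 cases; 489 / 0.6 = 815 subjects.
- Ratio 0.90: [0.20 / (0.85 × 0.90)] × [(1.645 + 0.842) / (ln(0.85/0.90) − ln 0.90)]² = 696 cases; 696 / 0.6 = 1,160 subjects.

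These are Wald figures. The score method needs about 840 and 1,205.

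**Range for the assumed agreement.** The same formulas with 5% discordance give 118 cases (197 subjects) for 10 points and 174 cases (290 subjects) for ratio 0.90. With 25% they give 613 cases (1,022 subjects) and 870 cases (1,450 subjects). Closed-form power at 72 cases over 5–25% discordance runs from 62% down to 21% for 10 points, from 48% down to 18% for ratio 0.90, and from nearly 100% down to 94% for ratio 0.76.

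**The case against.** The strongest reply is that the intended rule can be inferred. The formal hypotheses, the derivation and the quantified pass/fail sentence agree on 0.76, and 5.9.3 powers the trial against that null. The 10% appears once, in parentheses, with no scale, derivation or test. The reversed sentence is evidently a slip, corrected by its own continuation and by the alternative hypothesis, and the superiority sentence is followed at once by the 0.76 bound. This stands as far as it goes: those two sentences are wording errors and 0.76 is the likelier intent. It does not remove the conflict with the stated primary hypothesis, because the result the plan expects meets one margin and fails the other.

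A second objection concerns the calculation. Section 5.8.1.3 defines a case by any positive sample and credits each modality with systematic plus its own targeted samples. On that definition no case can be missed by both, so the 0.025 cell must be zero; discordance becomes 0.15 + 0.10 = 25%, and 80% agreement among cases is impossible. That is correct. The main figures therefore rest on the targeted-only reading in 5.7.2 and 5.9.5. The conclusion does not depend on it: with 10% or 25% discordance, 57–73% of trials still pass 0.76 and fail 10% (Wald).

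It is also fair that 0.76 is the more lenient margin and that the documents do not settle which was meant. The sponsor has to confirm the choice.

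**Conclusion.** The concern holds. The plan carries two incompatible primary margins, plus one sentence that asks for superiority and one that reverses the rule. Under its own inputs the 0.76 rule succeeds in 93–95% of trials and a 10% rule in 18–26%, and in 69–75% of trials the two give opposite answers. These figures assume that the 80% agreement applies among cases and that sensitivity uses targeted samples only. Varying the agreement moves the 10% power and the required sample size considerably, but in every case 120 subjects are too few for a 10% margin. The contradiction should be resolved before outcome data are seen. The interval method, the 20% margin in 5.20 and the sample definition are secondary and are not needed for this conclusion.

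**What to change.** State one rule and use it in 5.7.2, 5.9.1 and 5.9.5. The 0.76 ratio is recommended because it alone has formal hypotheses and a reproducible derivation. Suggested text:

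> Non-inferiority is declared if the lower one-sided 95% confidence bound of the paired ratio Se(micro-US)/Se(mpMRI) is greater than 0.76.

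Then:

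1. Replace the 10% in 5.7.2 with this margin and name the scale.
2. Delete the superiority sentence in 5.9.5, or make it a follow-on test after non-inferiority is shown.
3. In the margin subsection of 5.9.1, say that the lower bound must exceed 0.76.
4. Align the 20% and 108-subject sentence in 5.20, or mark it as superseded.
5. Name a paired-ratio interval, for example a score interval. McNemar's test addresses equality (ratio 1) and does not define an interval for the ratio. At a true ratio of 0.76 (0.684 against 0.90, discordance 25–35%) the one-sided error is 4.6–4.9% for the score method and 6.3–7.4% for Wald.
6. Say in the same sentence which samples define sensitivity, because 5.7.2 and 5.9.5 refer to targeted samples and 5.8.1.3 to systematic plus targeted.

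**Cost.** If 0.76 is kept, this is wording only, with no extra subjects; the power in 5.9.3 should be restated as about 93% (score) under its own inputs. If 10% was intended, it is a redesign: about 815 to 1,160 subjects at 20% discordance, or 197 to 1,450 across 5–25% discordance and both scales.

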### **5.9.6 Provision for an interim analysis**

There are no plans for interim analysis during this clinical trial.

### **5.9.6 Criteria for the termination of the clinical investigation**

There are no plans to stop the investigation early due to either early success or early futility.

The investigation will be terminated if Exact Imaging withdraws financial support for this study. In this case, Exact Imaging shall promptly inform the Principal Investigator of the termination or suspension and the reason(s) for this.

If the investigation is terminated early, no follow-up with subjects is required, since the standard of care for patients anticipating prostate biopsy is not affected by early termination.

### **5.9.7 Procedures for reporting deviation from the statistical plan**

Where the analysis of case data does not handle unexpected data, Exact Imaging will establish a strategy to modify the analysis algorithm and apply it to all data. Such modifications will include validation of the algorithm prior to its acceptance for use.

These modifications will be updated and described in the CIP, and/or as in the final report (as appropriate) along with justification for them.

### **5.9.8 Specification of subgroups for analysis**

All analyses will be conducted on all enrolled and completed subjects. These analyses will also be repeated on the "As Intended" population, which includes only subjects for which there were no major protocol deviations.

A low risk sub-population is pre-specified for analysis. This population includes men meeting all of the following criteria:

1. PSA < 20ng/ml
2. PSAD < 0.15 ng/ml/cc
3. Negative DRE

### **5.9.9 Procedures that take into account all data**

Statistical analyses around study endpoints will not include data for subjects who are withdrawn (before or after their biopsy) or for whom the collected study data is incomplete.

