#### **5.4.6 Medical procedures**

Medical procedures to be performed in the study consist of subject preparation, imaging and prostate biopsy. The procedure will be the same for all subjects.

Prior to consent and biopsy, the subject will have been imaged using mpMRI according to the PI-RADS v2 protocol, per the inclusion criteria and standard of care. The radiologist's report must be completed before the biopsy procedure.

The detailed procedure is as follows:

1. Screening and consent visit
2. Biopsy visit:
  - a. Operator 1 (blinded to mpMRI images and report)
    - i. Administer IV sedation per site standard of care
    - ii. Scan with EV29L micro-ultrasound transducer (ExactVu system)
    - iii. Save sweep of prostate
    - iv. Record any suspicious regions (PRI-MUS 3+)
    - v. Measure prostate volume (optional)
    - vi. Targeted biopsy samples (from micro-ultrasound)
      1. Samples from each targeted lesion will be placed in a separate labeled jar to ensure they can be independently discussed on the pathology report
    - vii. Systematic biopsy samples (fill in up to 12 samples)
  - b. Operator 2 (unblinded to mpMRI images and report)
    - i. Align labeled mpMRI sequences with ultrasound using FusionVu software
    - ii. Save a full sagittal sweep through the prostate with mpMRI guidance active for retrospective evaluation
    - iii. Targeted biopsy samples (using mpMRI guidance)
      1. Samples from each targeted lesion will be placed in a separate labeled jar to ensure they can be independently discussed on the pathology report

c. Remove transducer, use site-specific standard post-biopsy follow-up

The biopsy procedure takes approximately 30 minutes. The subject is not required to come for additional clinic visits in the context of the study.

Biopsy results will be provided to the subject's physician as per standard of care. Further healthcare decisions and follow-up are outside the scope of this study. The subject's participation in the study is completed following the prostate biopsy.

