#### **5.8.1.3 Endpoints**

##### **Primary endpoint**

The primary endpoint is the presence of clinically significant prostate cancer (csPCa) in each subject. The per-subject presence of cancer will be determined based on a positive biopsy from any sample, targeted or systematic. Patient-level sensitivity for a given imaging modality will be determined through systematic biopsy results plus targeted samples taken using only that modality. In this way we approximate clinical reality of using a given modality for systematic plus targeted biopsy.

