### **5.8.1.6 Replacing subjects**

Case data for all enrolled study subjects will be included in the analyses. Because a subject's involvement ends following his biopsy procedure, and because it is not expected that a subject will drop-out after his biopsy procedure, the need to replace subjects is expected to be unlikely.

If a subject needs to be replaced, he will be consented as per processes described for all study subjects.

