### **5.8.3.8 Estimated time needed to select this number (i.e. enrolment period)**

The investigation is expected to take approximately 12 months in total. This is intended to provide Urology San Antonio with adequate time to enroll and study the projected number of subjects in the trial. A subject's participation in the investigation is completed following his prostate biopsy.

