### **5.9.2 Sample size**

The trial will include 120 subjects. It is not anticipated that additional subjects will be required, however if a subject drops out before the biopsy procedure they may be replaced as described in section 5.8.1.6.

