#### **5.9.10 Treatment of missing, unused data**

If a study subject withdraws from the main trial prior to having his biopsy, his consent form will be retained, and the reason for exclusion of the data will be handwritten on the form as "withdrawn prior to biopsy". Similarly, if a study subject withdraws from the main trial following his biopsy, his consent form and CRF will be retained, and both will be marked "withdrawn following biopsy".

This will allow data to be collected about the number of patients that withdrew from the investigation prior to the biopsy procedure, and the number that withdrew after the procedure.

The same process will be applied to any circumstance of incomplete or incorrect data, with an indicator handwritten on his consent form and CRF to provide information about why the record is not used for analysis.

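### Section 5.9.9 leaves men who withdraw after biopsy out of the endpoint analyses, although nothing more is needed from them, and contradicts section 5.8.1.6

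*Combined protocol and SAP*

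**What the plan says.** Four places in the combined protocol and SAP bear on who is analysed.

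- Section 5.9.9: "Statistical analyses around study endpoints will not include data for subjects who are withdrawn (before or after their biopsy". It also leaves out subjects whose study data are incomplete.
- Section 5.9.10: "if a study subject withdraws from the main trial following his biopsy, his consent form and CRF will be retained". Both documents are marked to show the withdrawal, and the record is treated as unused.
- Section 5.8.1.6: "Case data for all enrolled study subjects will be included in the analyses".
- Section 5.9.8: "All analyses will be conducted on all enrolled and completed subjects". The word *completed* is not defined there.

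On timing, section 5.4.6 says "The subject's participation in the study is completed following the prostate biopsy", and section 5.8.3.8 says the same of the investigation: "A subject's participation in the investigation is completed following his prostate biopsy". Section 5.8.4.4 provides for no follow-up. Section 5.8.3.3 lets a subject withdraw at any time.

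On the endpoint, section 5.8.1.3 says: "The per-subject presence of cancer will be determined based on a positive biopsy from any sample, targeted or systematic".

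On replacement, section 5.9.2 says "if a subject drops out before the biopsy procedure they may be replaced as described in section 5.8.1.6". Section 5.8.1.6 states no such limit and adds that drop-out after biopsy is not expected.

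**The concern.** A rule that leaves out subjects with no endpoint data needs little defence. This rule also leaves out men whose endpoint data have been obtained or are about to be. Once the biopsy visit is over, both operators have taken their cores and the paired comparison for that man needs only the pathology report. Withdrawal has no deadline, so it may come after that report. An exclusion that can follow the result can depend on the result, and the plan has no sensitivity analysis that puts these men back. The *As Intended* repeat in section 5.9.8 only removes more.

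The primary measure is a ratio of paired sensitivities, and its distance from 1 is driven by the men in whom only one modality finds clinically significant cancer. There are few of them. The sponsor makes the device, funds the study and monitors it, so an avoidable exclusion of this kind would draw questions. A statistician programming the analysis would also have to choose between sections 5.8.1.6 and 5.9.9.

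**Working it through.** **The passages side by side.** Take a man who has both sets of cores taken and then withdraws.

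| Section | Is he analysed? |
|---|---|
| 5.8.1.6 | Yes, as an enrolled subject |
| 5.9.9 | No, withdrawn after biopsy |
| 5.9.10 | No; records kept and marked |
| 5.9.8 | Yes if *completed* means biopsy done (5.4.6, 5.8.3.8); no if it means not withdrawn |

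Sections 5.8.1.6 and 5.9.9 conflict directly. Section 5.9.8 fits either, depending on the undefined word.

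**Inputs.** N = 120 and 60% prevalence give 72 men with csPCa. Sensitivities are 0.85 (micro-ultrasound) and 0.90 (mpMRI), with 80% agreement (5.9.1, 5.9.3). The margin is a ratio of 0.76 with a one-sided 95% bound (5.9.5). The plan gives no rate of post-biopsy withdrawal, so there is no plan figure for this effect to reproduce. (The stated 80% power at N = 120 does not reproduce: these inputs give 93.3% by a score test and 97.5% by Wald. That is a separate matter and does not affect this point.)

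**Cells.** Discordance is 20% and the sensitivities differ by 5 points, so mpMRI only = (0.20 + 0.05)/2 = 0.125 and micro-ultrasound only = 0.075. Then both = 0.85 − 0.075 = 0.775 and neither = 0.025. Times 72: a = 55.8 both, b = 5.4 micro-ultrasound only, c = 9.0 mpMRI only, 1.8 neither.

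**Formula.** Ratio R = (a + b)/(a + c); SE of log R = √[(b + c)/((a + b)(a + c))]; lower bound = R × exp(−1.645 × SE). The plan names McNemar's test for the interval but gives no formula, so the log-ratio Wald form is an assumption.

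**Under the plan's inputs.** With nobody removed, R = 61.2/64.8 = 0.944, SE = √[14.4/(61.2 × 64.8)] = 0.0603, bound 0.855.

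| Removed | mpMRI-only men: R, bound | micro-ultrasound-only men: R, bound |
|---|---|---|
| 1 | 0.959, 0.871 | 0.929, 0.844 |
| 2 | 0.975, 0.888 | 0.914, 0.832 |
| 3 | 0.990, 0.905 | 0.898, 0.820 |

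Every bound is above 0.76, so the conclusion does not change.

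**A borderline result (illustrative).** Take 46 both, 4 micro-ultrasound only, 14 mpMRI only, 8 neither.

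- Nobody removed: R = 50/60 = 0.833; SE = √[18/(50 × 60)] = 0.0775; bound 0.734, fails.
- Two mpMRI-only men removed: R = 50/58 = 0.862; SE = √[16/(50 × 58)] = 0.0743; bound 0.763, passes.

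As a check on the choice of test, use the constrained score statistic T = √n (p1 − 0.76 p0)/√[0.76 (s10 + s01)], where p1 and p0 are the micro-ultrasound and mpMRI sensitivities and s10, s01 are the discordant proportions estimated at ratio 0.76. It passes if T > 1.645.

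| mpMRI-only men removed | n | p1, p0 | s10 + s01 | T |
|---|---|---|---|---|
| 0 | 72 | 0.694, 0.833 | 0.290 | 1.10 |
| 2 | 70 | 0.714, 0.829 | 0.285 | 1.52 |
| 3 | 69 | 0.725, 0.826 | 0.282 | 1.74 |

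So this table crosses the margin after two losses by Wald and after three by the score test.

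**Error rate under selective loss.** Simulation at a true ratio of 0.76 (mpMRI 0.90, micro-ultrasound 0.684; discordance assumed 25% or 30%; 400,000 runs each) gives one-sided score-test error of 4.7–4.8% with no loss. It rises to 6.5–6.7% if 5% of mpMRI-only men are lost (about one man) and 9.0–9.3% if 10% are lost (about two). These loss rates are assumptions. Loss unrelated to outcome does little: at 10% loss, score-test power falls from 93.3% to 90.7%.

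**The case against.** The strongest reply is that this will hardly ever happen. Section 5.8.1.6 expects no drop-out after biopsy, and with no visits or follow-up afterwards a man has little reason to withdraw. Withdrawal is also traceable: section 5.8.3.3 has the subject notify the Principal Investigator, section 5.8.5(i) has it documented and reported, section 5.12 has the reason recorded, and section 5.9.10 already counts withdrawals before and after biopsy. All of that stands. It limits the size of the problem but does not remove the contradiction, and recording an exclusion does not undo it.

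A reader might also infer more than the documents support:

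- *That the result is always known when the man is removed.* The cores exist at that point, but pathology may be pending. It is known only if he withdraws after the report.
- *That data are destroyed.* They are left out of analysis; the CRF is kept.
- *That the sponsor or investigator may remove a man at will.* The passive wording in 5.9.9 and the mention of discontinuation in the heading of 5.8.3.3 are loose, but the only withdrawal described is the subject's own.
- *That a biopsied man may be replaced.* Section 5.9.2 speaks of drop-out before biopsy. Section 5.8.1.6 is ambiguous but describes no replacement after biopsy.
- *That sections 5.9.8 and 5.9.9 plainly conflict.* Section 5.9.9 can be read as saying who has not completed; then 5.9.8, 5.9.9 and 5.9.10 agree and only 5.8.1.6 is out of line.
- *That the type I error is inflated as the plan stands.* The simulated rates assume that only mpMRI-only men are lost. Loss of micro-ultrasound-only men pushes the other way. A Wald test also overstates the level: with an assumed 5% micro-ultrasound-only cell it runs at 6.6% with nobody removed.

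**Conclusion.** The point holds as a contradiction between sections 5.8.1.6 and 5.9.9, and as a rule that sets aside paired outcomes that have been or will be observed. Section 5.9.8 sits uneasily with 5.9.9 because sections 5.4.6 and 5.8.3.8 place completion at the biopsy, but that conflict depends on an undefined term.

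Outcome-dependent exclusion is something the rule leaves open; nothing shows that it is intended or likely. Under the plan's inputs, up to three lost discordant men would not alter the conclusion. Near the margin, two or three men lost in one direction could alter it, the number depending on the test used. These sizes rest on the 72-man expectation, the assumed test and, for the borderline case, an illustrative table. The correction is worth making because it costs almost nothing and should precede any knowledge of results.

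**What to change.** Amend section 5.9.9 along these lines: *Subjects withdrawn before any study core is taken are not analysed. For subjects who withdraw after biopsy, data collected up to withdrawal, including pathology on cores already taken, remain in the primary analysis unless the subject asks for his data to be removed. Such cases are listed by modality result.*

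Keep a separate statement on incomplete data, so that the existing clause is not lost in the rewrite.

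Align the related sections: restate the analysis set in 5.8.1.6, define *completed* in 5.9.8, and change 5.9.10 so that a post-biopsy withdrawal is not automatically an unused record. In 5.8.1.6 and 5.9.2, state that only subjects lost before biopsy are replaced.

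The cost is wording in five sections and a check that the consent form permits use of data collected before withdrawal. No extra subjects or procedures are needed. The one downside is that a man who withdraws after biopsy and asks for his data to be removed is not topped up.
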